7.4.5 Secondary Efficacy Endpoints Analysis Methods

7.4.5.1 Transfusion Independence

TI is defined as a period of at least 56 days with no RBC or platelet transfusion since the date of randomization to the last dose of study drug + 30 days, the initiation of posttreatment therapy, or death, whichever occurs first. The overall TI rate (based on receiving neither RBC nor platelet transfusion for post-baseline period of any at least 56 days) with respective 95% exact binomial CIs based on the Clopper-Pearson exact method will be calculated by treatment group. The stratified CMH test will be applied to compare the TI rates between the 2 treatment groups. The RBC TI rate and the platelet TI rate, along with 95% exact binomial CIs, will also be calculated and summarized by treatment group. Analyses of the TI rates will be based on the mITT analysis set.

A by-participant listing of the derived efficacy data used for determining the TI rate will be provided.

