The primary endpoint will be tested at a full alpha level of 2.5%. To control the overall Type I error rate of the primary and key secondary endpoints, hierarchical testing will be performed in the following order: (1) primary endpoint; (2) key secondary endpoint. If hypothesis testing of the primary endpoint is rejected, the key secondary endpoint will be tested at the full alpha level of 2.5%; otherwise, the testing will be stopped. Secondary and exploratory efficacy endpoints will be tested using a two-sided, 5% significance level, and two-sided 95% CIs will be reported when appropriate, unless otherwise specified. P-values will be rounded to 4 decimal places. P-values less than 0.0001 will be displayed as "<0.0001"; p-values greater than 0.9999 will be displayed as ">0.9999".

When applicable, analyses will be stratified by IPSS-R risk group (Intermediate, High, and Very High Risk) and by geographical region (North America, Western Europe, plus Israel, and Eastern Europe).

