7.3.8 Prior and Concomitant Blood Transfusions

Any transfusions from 16 weeks prior to randomization through the Disease Follow-up period will be recorded. Transfusions will be classified as prior or concomitant based on the start date. A prior transfusion is defined as any transfusion that started up to 16 weeks prior to the date of randomization. A concomitant transfusion is defined as any transfusion that started on or after the date of randomization through the Disease Follow-up period. Prior and concomitant blood transfusions will be summarized separately.

For both prior and concomitant transfusion summaries, the number and percentage of participants receiving any RBC or platelet transfusion will be summarized by treatment group and overall, as will the number and percentage by transfusion type (RBCs, platelets, or other blood product). Participants with more than 1 transfusion at each level of summarization (any transfusion received, transfusion type) will be counted only once. Additionally, transfusion burden (units/56 days) will be summarized using descriptive statistics as part of the prior transfusion and concomitant blood transfusion units received from 16 weeks prior to randomization to randomization for prior transfusion, and the total number of transfusion units received from randomization through Disease Follow-up period for concomitant blood transfusion. Transfusion burden will be analyzed by each 56 days blocks for both prior transfusion and concomitant blood transfusion. The study phase during which each transfusion was received (e.g., prior or concomitant) will be presented on the listing of blood transfusions.

mITT and ITT analysis sets will be used for prior and concomitant blood transfusions analysis.

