7.4.2 Strata Pooling Strategy

There are a total of 6 strata as follows:

- Very high & North America, Western Europe, and Israel
- High & North America, Western Europe, and Israel
- Intermediate & North America, Western Europe, and Israel
- Very high & Eastern Europe
- High & Eastern Europe
- Intermediate & Eastern Europe

For stratified analysis of any efficacy endpoint, the following steps will be used to pool strata if there is insufficient information in any one stratum.

Step 1: First look at the region strata, if any region stratum <6 participants, this stratum will be pooled to the opposite region stratum with a higher number (e.g., if Very high & Eastern Europe = 2 participants and Very high & North America, Western Europe, and Israel = 3 participants, then 2 participants will be pooled with 3 participants). If there is a tie, then Eastern Europe will be pooled to North America, Western Europe, and Israel. (e.g., if Very high &Eastern Europe = 2 participants and Very high &North America, Western Europe and Israel = 2 participants, Eastern Europe will be pooled to Very high &North America, Western Europe, and Israel = 2 participants, Eastern Europe will be pooled to Very high &North America, Western Europe, and Israel = 2 participants, Eastern Europe will be pooled to Very high &North America, Western Europe, and Israel = 2 participants, Eastern Europe will be pooled to Very high &North America, Western Europe, and Israel).

Step 2: If any stratum is <6 participants after Step 1, then the following strategy of pooling will be taken in order of:

Very High pool to High from the same region (e.g., if Very high & North America, Western Europe, and Israel is <6 participants, then it will be pooled to High & North America, Western Europe, and Israel)

High pool to Very High from the same region

Intermediate pool to High from the same region.

Step 3: If any stratum is <6 participants after Step 2, then repeat Step 1 and Step 2.

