7.4.6.7 Transfusion Rate

Participants who have been on treatment for at least 56 days are considered evaluable for this analysis.

Definitions:

• Baseline Transfusion Dependence:

Transfusion of ≥ 1 unit of RBCs and/or platelets during the 56 days prior to date of randomization.

• Baseline TI:

No RBC or platelet transfusions during the 56 days prior to date of randomization.

• Post-baseline TI:

Post-baseline TI is defined as a period of at least 56 days with no RBC or platelet transfusion since the date of randomization to the last dose of study drug + 30 days, the initiation of post-treatment therapy, or death, whichever occurs first.

Analyses:

The mITT Analysis Set will be used for the following transfusion rate analyses.

Overall transfusion status (RBC or platelets), RBC transfusion status, and platelet transfusion status will be analyzed separately as below:

• Rate of conversion of baseline transfusion dependence to post-baseline TI in the baseline transfusion-dependent mITT participants.

The number and percentage of mITT participants who are transfusion dependent at baseline and the number and percentage of baseline transfusion-dependent mITT participants who achieved post-baseline TI, along with respective 95% exact binomial CIs, will be summarized by treatment group.

• Rate of maintenance of baseline TI in the baseline transfusion-independent mITT patients.

The number and percentage of mITT participants who are transfusion independent at baseline and the number and percentage of baseline transfusion-independent mITT participants who maintained TI post-baseline will be summarized by treatment group.

In addition, the median number of units of RBC and platelets received in 56 days blocks (e.g., Day 1 to Day 56, Day 57 to Day 112, and etc.) starting from Cycle 1 Day 1 will be reported for each treatment group.

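### The test of transfusion independence leaves out baseline transfusion status, which the trial records and defines, so it can lose power and is open to chance imbalance between the arms.

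*SAP*

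**What the plan says.** SAP 7.4.5.1 (and Protocol 9.4.4) compares TI between arms: "The stratified CMH test will be applied to compare the TI rates between the 2 treatment groups". The analysis set is mITT: "Analyses of the TI rates will be based on the mITT analysis set". The level comes from SAP 7.1.1: "Secondary and exploratory efficacy endpoints will be tested using a two-sided, 5% significance level", outside the CR-then-OS hierarchy.

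SAP 7.1.1 fixes the strata: where applicable, "analyses will be stratified by IPSS-R risk group (Intermediate, High, and Very High Risk) and by geographical region". SAP 7.4.2 lists them ("There are a total of 6 strata as follows") and pools sparse ones: "if any region stratum <6 participants, this stratum will be pooled to the opposite region stratum with a higher number". Baseline transfusion status appears in neither place.

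The baseline information exists. SAP 7.3.8 says "Any transfusions from 16 weeks prior to randomization through the Disease Follow-up period will be recorded". SAP 7.4.6.7 defines baseline dependence as one unit or more in the 56 days before randomization, and baseline independence as "No RBC or platelet transfusions during the 56 days prior to date of randomization". That definition is used only for exploratory summaries by arm: conversion to TI among baseline-dependent participants and maintenance of TI among baseline-independent ones.

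**The concern.** The omitted baseline factor is the endpoint state itself, measured over the same 56-day length. A participant who needed no transfusion before entry can meet TI simply by staying that way, with no drug effect. Two consequences follow.

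- **Power.** Outcome variation explained by baseline status stays in the error term, and the marginal treatment effect is diluted relative to the effect within baseline groups.
- **Imbalance.** Baseline status is not a randomization factor, so any chance difference between arms passes into the TI difference uncorrected.

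SAP Table 5 states the TI objective as demonstrating superiority. A TI result that can be answered by saying the arms differed at entry serves that objective poorly.

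**Working it through.** **Inputs from the documents**
- N: Protocol 9.4.2 places the CR analysis at 190 patients. SAP 7.4.7.1 places the CR futility look at the 95th participant and information fraction 0.5, and 95/0.5 = 190. The mITT size is redacted, so 190 is used for it.
- Allocation 2:1, hence about 127 v 63; blocks of 6 (Protocol 4.1).
- Six strata, two-sided 5%, CMH test.

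The plan gives no TI rate, effect size or power, so there is no figure to reproduce. Everything below that uses TI rates is an assumption.

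**Correlation of baseline status with TI.** With share q dependent, control TI rates p_I (independent) and p_D (dependent), and overall rate p:

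rho = (p_I − p_D) × sqrt(q(1−q)) / sqrt(p(1−p)).

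For 75% v 25% and q = 0.5: 0.50 × 0.5/0.5 = 0.50.

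**Rough power check.** Adjustment multiplies the variance by about 1 − rho² = 0.75. A planned power of 70% corresponds to z = 1.960 + 0.524 = 2.484. Then 2.484/sqrt(0.75) = 2.869, and 2.869 − 1.960 = 0.909, which is power of about 82%.

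**Simulation, set 1.** 3,000 trials per row, N = 190, stratified blocks of 6, conditional odds ratio e^1.0 = 2.72. CMH on 6 strata was compared with CMH on 6 strata × baseline status.

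| Control TI, independent v dependent | rho | Power, planned | Power, with baseline status | Null rejection, planned / with status |
|---|---|---|---|---|
| 75% v 25% | 0.50 | 68.6% | 78.6% | 5.6% / 5.4% |
| 80% v 30% (60% dependent) | 0.49 | 71.3% | 78.7% | 4.9% / 4.7% |
| 70% v 30% | 0.40 | 75.3% | 80.3% | 4.9% / 4.8% |
| 65% v 40% | 0.25 | 84.1% | 84.6% | 4.5% / 4.6% |

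**Simulation, set 2.** 8,000 trials per row, other assumed rates, odds ratio 2.5, 12 cells without pooling.

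| Share dependent; control TI, dependent v independent | Planned | With baseline status |
|---|---|---|
| 50%; 25% v 65% | 70.9% | 75.9% |
| 50%; 20% v 75% | 55.3% | 68.3% |
| 60%; 20% v 70% | 61.5% | 71.4% |
| 40%; 30% v 70% | 68.7% | 73.7% |
| 50%; 30% v 50% (weak) | 81.5% | 81.6% |
| 50%; 15% v 85% (extreme) | 35.5% | 56.0% |

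Over odds ratios of 2 to 3, the first four rows gain about 4 to 13 points. Letting dependence rise with IPSS-R category (0.15 per category, first row) gives 70.3% v 75.3%, so the IPSS-R stratum does not stand in for the missing factor.

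**Chance imbalance.** SD = sqrt(q(1−q)(1/127 + 1/63)). At q = 0.5 this is sqrt(0.25 × 0.02375) = 0.077, or 7.7 points. Two SDs are 15.4 points. Multiplied by a 40-point gap in TI between baseline groups this shifts the TI difference by 6.2 points; by a 50-point gap, 7.7 points. An imbalance of at least 10 points in either direction has a probability of about 19%.

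Among simulated null trials with such an imbalance, the planned test rejects in about 9% to 12% (first four rows of set 2), against about 5% to 6% when baseline status is a stratum. In the first row at odds ratio 2.5, the planned test's power is 47% when the tamibarotene arm has at least 10 points more dependent participants and 90% when it has at least 10 points fewer. The stratified test stays at 76% to 77% in both.

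**The case against.** The strongest reply is that nothing here is an error. The CMH test on the randomization strata is valid, and its overall type I error is about 5%; the imbalance problem concerns the reading of one realized trial. TI is outside the alpha hierarchy, is not powered in either sample-size section, and cannot change the CR or OS conclusion. All of that stands, and it limits the importance of the point.

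The size is also assumed. Baseline dependence needs only one unit in 56 days, and TI needs only one 56-day window over the whole treatment period, so baseline status may be less prognostic than the larger scenarios suppose. Other equally unsupported scenarios gain little: a 30-point gap with 50% dependent gives 82.4% to 84.9%, and a 40-point gap with 80% dependent gives 82.3% to 85.1%. The 2-SD imbalance is a tail case, reached in about 5% of trials.

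The SAP does look at baseline status elsewhere. SAP 7.4.6.7 reports conversion and maintenance by arm, and SAP 7.3.8 tabulates prior transfusions, so an imbalance would be visible. But these outputs are descriptive and name no between-arm test, and the 7.4.6.7 summaries count only participants treated for at least 56 days, a condition set after randomization. The subgroup analyses in SAP 7.4.7.3 cover CR and OS, and SAP 7.4.1 does not list TI among the endpoints with an ITT sensitivity analysis. Seeing an imbalance is not the same as having a prespecified comparison that allows for it.

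The last objection, that the fix needs a rule for missing baseline status, is right and is taken up below.

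**Conclusion.** The concern holds. The only formal test of TI omits a baseline measurement of the same state that the trial already collects and defines, and no other planned analysis supplies an adjusted comparison. The omission is certain; its cost is not. If baseline status is clearly prognostic (a gap of about 40 to 55 points in control TI), the loss is about 4 to 13 points of power at N = 190. If it is weakly prognostic, the loss is close to zero, and adjusting costs nothing visible. The adjusted test holds its size (4.6% to 5.4% null rejection in set 1). Exposure to imbalance follows from the arm sizes and an assumed dependent share near one half: SD 7.7 points, with roughly a one-in-five chance of 10 points or more. This is a worthwhile improvement to a supportive endpoint, not a defect in the primary or key secondary analysis.

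**What to change.** In SAP 7.4.5.1, before unblinding:

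1. Run the TI CMH test with baseline transfusion status (dependent v independent, by the SAP 7.4.6.7 definition, for all mITT participants) as an additional stratum within IPSS-R × region.
2. Apply the SAP 7.4.2 pooling steps within each baseline status.
3. Report the Mantel-Haenszel-weighted TI difference with the test.
4. State where participants with missing baseline status go. SAP 7.1.3.9 leaves such status missing without imputation; a missing category or a stated default would settle it.
5. Keep the present six-stratum test as a sensitivity analysis.

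One data point should be reconciled at the same time. Footnote (w) of the Protocol Schedule of Activities limits the red-cell transfusions entered in the eCRF to those given at a hemoglobin of 9 g/dL or below, while Protocol 8.1.5 says all are recorded. This affects baseline status and the TI endpoint alike.

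The cost is a short SAP edit and a few lines of code, with no new data collection. The downside is up to 12 strata before pooling (about 190/12 = 16 participants each on average), which the CMH test tolerates.

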7.4.5.2 Overall Response

The ORR is defined as achievement of CR, PR, mCR, or HI as determined by the investigator per the modified IWG MDS criteria (Cheson 2006).

The following analyses will be conducted separately:

- [1] Primary analysis of ORR estimand (investigator response in mITT analysis set)
- [2] Sensitivity analysis of ORR estimand (investigator response in ITT analysis set)

The ORR and 95% exact binomial CIs based on the Clopper-Pearson exact method will be calculated and summarized by treatment group. The stratified CMH test will be applied to compare the ORRs between the 2 treatment groups.

The number and percentage of participants and 95% exact binomial CIs based on the Clopper-Pearson exact method for the individual rates of CR, PR, mCR, and HI; combined rates of CR or PR; combined rates of CR or mCR; combined rates of CR, PR, or mCR; combined rates of CR, mCR, PR, and HI (for participants who failed to achieve

CR, mCR, or PR); and categories of HI (for participants who failed to achieve CR, mCR, or PR) will also be summarized.

For participants who had mCR, the subcategories of mCR with HI and mCR without HI will be summarized. mCR with HI is defined as achieving both mCR and HI as determined by the investigator per the modified IWG MDS criteria (Cheson 2006), whereas mCR without HI is defined as achieving mCR but not HI (based on the same IWG MDS criteria).

CR and overall response may also be analyzed in line with the proposed revised IWG response criteria for HR-MDS (Zeidan 2023). A by-participant listing of the derived efficacy data used for determining the ORR will be provided.

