9.4.4 Secondary Endpoints

Transfusion Independence

TI, defined as a period of at least 56 days with no RBC or platelet transfusion since the date of randomization to the last dose of study drug +30 days, the initiation of post-treatment therapy, or death, whichever occurs first.

TI rate (based on receiving neither RBC nor platelet transfusion for a period of at least 56 days) with respective 95% exact binomial CIs will be calculated by treatment group. The stratified CMH test will be applied to compare the TI rates between the 2 treatment groups.

Overall Response

Overall response, defined as achievement of CR, PR, marrow CR (mCR), or HI as determined by the investigator per the modified IWG MDS criteria (Cheson 2006).

Overall response rate (ORR) and 95% exact binomial CIs will be calculated by treatment group. The stratified CMH test will be applied to compare the ORRs between the 2 treatment groups. The rates of CR or PR; rates of CR, PR, or marrow CR; and the rates of HI will also be summarized with 95% exact binomial CIs and compared between the treatment groups using the stratified CMH test.

Overall response may also be analyzed in line with the updated IWG response criteria (Zeidan 2023).

Duration of Complete Remission

DOCR, defined as the duration from the date of first documented evidence of CR to the date of documented relapse of disease, as determined by the investigator per the modified IWG MDS criteria (Cheson 2006), or death due to any cause, whichever occurs first.

Kaplan-Meier estimation of median DOCR and corresponding 95% CIs will be presented by treatment group.

Duration of Overall Response

Duration of overall response defined as the duration from the date of first documented evidence of CR, PR, mCR, or HI, to the date of documented disease progression, relapse of disease as determined by the investigator per the modified IWG MDS criteria (Cheson 2006), or death due to any cause, whichever occurs first.

Kaplan-Meier estimation of median duration of overall response and corresponding 95% CIs will be presented by treatment group.

Time to CR

Time to CR, defined as the duration from the date of randomization to the date of the first documented evidence of CR as determined by the investigator per the modified IWG MDS criteria (Cheson 2006).

Time to CR will be summarized descriptively for the 2 treatment groups.

Time to Initial Response

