6.4.1.3 Secondary Efficacy Endpoints and Estimands

The secondary efficacy endpoints are:

• TI, defined as a period of at least 56 days with no red blood cell (RBC) or platelet transfusion since the date of randomization to the last dose of study drug + 30 days, the initiation of post-treatment therapy, or death, whichever occurs first. TI rate is calculated as:

TI rate (%) = number of participants who achieve TI / number of participants in the mITT analysis set \times 100. The denominator is the mITT population in each treatment group.

• Overall response, defined as achieving CR, partial remission (PR), marrow CR (mCR), or subcategories of hematologic improvement (HI), as determined by the investigator per the modified IWG MDS criteria (Cheson 2006). ORR will be calculated as:

ORR (%) = number of overall responders / number of participants in the mITT analysis set \times 100. The denominator is the mITT population in each treatment group.

Overall response may also be analyzed in line with the updated IWG response criteria (Zeidan 2023).

• DOCR, defined as the duration from the date of first documented evidence of CR to the date of documented relapse of disease or disease progression, as determined by the investigator per the modified IWG MDS criteria (Cheson 2006), or death due to any cause, whichever occurs first. Among CR responders, DOCR will be calculated in months as:

DOCR (months) = (first date of documented relapse of disease, disease progression, or death due to any cause - date of first documented evidence of <math>CR + 1) / 30.4375.

• Duration of overall response, defined as the duration from the date of first documented evidence of CR, PR, mCR, or HI, to the date of documented disease progression or relapse of disease, as determined by the investigator per the modified IWG MDS criteria (Cheson 2006), or death due to any cause, whichever occurs first. Among overall responders, duration of overall response will be calculated in months as:

Duration of overall response (months) = (first date of documented disease progression, relapse of disease, or death due to any cause - date of first documented evidence of CR, PR, mCR, or HI + 1) / 30.4375.

• Time to CR, defined as the duration from the date of randomization to the date of the first documented evidence of CR as determined by the investigator per the modified IWG MDS criteria (Cheson 2006). Among CR responders, this endpoint will be calculated as:

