6.4.1.4 Exploratory Efficacy Endpoints

The exploratory efficacy endpoints are:

• Cytogenetic CR, defined as participants achieving cytogenetic CR (Cheson 2006), as determined by the investigator. The cytogenetic CR rate will be calculated as:

Cytogenetic CR rate (%) = number of cytogenetic CR responders / mITT participants with baseline cytogenetics abnormality \times 100.

- Molecular response, defined as participants achieving a reduction in variant allele frequency by next-generation sequencing.
- Transfusion requirement, defined as the frequency and amount of blood products (RBC or platelet) received.
- The rate of consolidation with allogeneic HSCT is defined as the proportion of participants who are treated with allogeneic HSCT. This endpoint is calculated as:

Consolidation with allogeneic HSCT rate (%) = number of participants treated with allogeneic HSCT / number of participants in the mITT analysis set \times 100. The denominator is the mITT population in each treatment group.

• Clinical response and genetic mutations and/or gene expression markers at baseline, at the time of response, and loss of response.

Response types (i.e., CR, PR, mCR, etc.) included in the efficacy endpoints are defined in Table 7 and Table 8. A sample of the EORTC QLQ-30 can be found in Appendix 9, and a sample of the EQ-5D-5L can be found in Appendix 10 of the Study SY-1425-301 protocol.

Response Criteria ^a		Peripheral	Blood		BMB (%)	Other
	Hemoglobin	Neutrophils	Platelets	Blasts		
	(g/dL)	per (L)	per (L)	(%)		
CR	≥11	$\geq 1.0 \times 10^9$	$\geq 100 \times 10^9$	0	≤5	Normal maturation of all cell lines, persistent dysplasia will be noted

Table 7IWG Response Criteria for MDS

Syros Pharmaceuticals, Inc.

SY-1425-301

Response Criteria ^a		Peripheral	Blood		BMB (%)	Other
Crueriu	Hemoglobin	Neutrophils	Platelets	Blasts		
	(g/dL)	per (L)	per (L)	(%)		
PR					Decreased by ≥50% from baseline, but >5%	All CR criteria if abnormal before treatment except BMB
mCR	If HI response, note in addition to mCR				Decreased by \geq 50% from baseline, and \leq 5%	
Stable disease						Failure to achieve PR and no evidence of progression for >8 weeks
Failure						Death during treatment, or disease progression: worsening cytopenia, increase in % BMBs, progression to a more advanced MDS FAB subtype

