Relapse after CR or PR						At least one of the following: Return to pretreatment BMB %. Decrement of ≥50% from maximum remission/response levels in granulocytes or platelets. Reduction in Hgb ≥1.5g/dL or transfusion dependence.
Cytogenet	Cytogenetic Response			1	1	1
Complete Partial			Disappearance of chromosomal abnormality with no appearance of new ones. ≥50% reduction of chromosomal abnormality			

Response Criteriaª		Peripheral Blood			BMB (%)	Other	
	Hemoglobin	Neutrophils	Platelets	Blasts			
	(g/dL)	per (L)	per (L)	(%)			
Disease Progression, participants with:		Evaluation C	Evaluation Criteria:				
<5% bone marrow blasts		\geq 50% increase to >5% bone marrow blasts					
5%-<10% l	bone marrow bla	sts	\geq 50% increase to >10% bone marrow blasts				
10%-<20%	0% -<20% bone marrow blasts \geq 50% increase t			e to ≥20%	bone marrow b	lasts	
For all categories			At least 50% decrease from maximum remission/response in granulocytes or platelets				
			or reduction in Hgb by ≥ 2 g/dL or transfusion dependence				

Abbreviations: BMB = bone marrow blasts; CR = complete remission; FAB = French-American-British; HI = hematologic improvement; Hgb = hemoglobin; IWG = International Working Group; mCR = marrow CR; MDS = myelodysplastic syndrome; PR = partial remission ^a Response must last at least 4 weeks.

The IWG criteria for HI define specific responses of cytopenias in the 3 hematopoietic lineages: erythroid (HI-E), platelet (HI-P), and neutrophil (HI-N). The HIs are measured in participants with pretreatment abnormal values: hemoglobin level less than 110 g/L (11 g/dL) or RBC-transfusion dependence, platelet count less than 100×10^9 /L or platelet-transfusion dependence, and absolute neutrophil count (ANC) less than 1.0×10^9 /L.

Table 8 Response Criteria for Hematologic Improvement for MDS

Hematologic Improvement	Response Criteria (Response Lasting 8 Weeks)
Erythroid response (pretreatment <11 g/dL)	Hgb increase by $\geq 1.5 \text{ g/dL}$
	Relevant reduction of units of RBC transfusions by an absolute
	number of at least 4 RBC transfusions/8 weeks compared with
	the pretreatment transfusion number in the previous 8 weeks.
	Only RBC transfusions given for a Hgb of $\leq 9.0 \text{ g/dL}$
	pretreatment will count in the RBC transfusion response
	evaluation.
Platelet response (pretreatment $<100 \times 10^{9}/L$)	Absolute increase of $\geq 30 \times 10^{9}$ /L if starting with $\geq 20 \times 10^{9}$ /L
	platelets

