7.4 Efficacy Evaluation

7.4.1 Datasets Analyzed

All efficacy summaries, except for OS and EFS, will be based on the mITT analysis set. An additional summary of the primary endpoint CR will be based on the PP analysis set. The OS and EFS analyses will be based on the ITT analysis set. The ITT analysis set will be used for sensitivity analyses of efficacy endpoints, including CR, ORR, DOCR, duration of overall response, time to CR, and time to initial response. Efficacy endpoints will be based on all disease assessments during the study, unless otherwise specified.

Listings of MDS disease response assessments, hematology laboratory results, bone marrow morphology and cytogenetics results, and post-treatment survival follow-up will be provided to support the efficacy analyses.

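### HI by lineage is summarized only for participants without CR, mCR or PR, and with no stated denominator, so it cannot show the treatment effect on blood counts

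*SAP*

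**What the plan says.** - **SAP 7.4.5.2, lineage lines.** The list of response summaries ends with "and categories of HI (for participants who failed to achieve CR, mCR, or PR) will also be summarized". The section gives no denominator for these lines.
- **SAP 7.4.5.2, other HI lines.** The same sentence plans "Clopper-Pearson exact method for the individual rates of CR, PR, mCR, and HI", where HI carries no restriction. The next paragraph adds: "For participants who had mCR, the subcategories of mCR with HI and mCR without HI will be summarized". That split is by presence of HI, not by lineage.
- **SAP 7.4.1, default set.** "All efficacy summaries, except for OS and EFS, will be based on the mITT analysis set". For ORR, SAP 6.4.1.3 writes the denominator out: "ORR (%) = number of overall responders / number of participants in the mITT analysis set".
- **SAP 6.4.1.4, who can have HI.** The text after Table 7 defines HI by three lineages (HI-E, HI-P, HI-N) and says "The HIs are measured in participants with pretreatment abnormal values". For cytogenetic CR the same section names a restricted denominator: "mITT participants with baseline cytogenetics abnormality".
- **Protocol 9.4.4.** For HI without restriction: "the rates of HI will also be summarized with 95% exact binomial CIs and compared between the treatment groups using the stratified CMH test". SAP 7.4.5.2 names the stratified CMH test only for ORR.

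**The concern.** Whether a participant achieves CR, PR or mCR is decided after randomization and is what the drug is meant to change. CR itself requires hemoglobin, neutrophils and platelets above set levels (SAP Table 7), so the restriction removes participants with the best counts, and removes more of them from the more effective arm. No section plans HI by lineage for remission responders. A reader who goes to the HI-E, HI-P and HI-N lines for the effect on anemia, platelets or neutrophils would see only a residual category.

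The missing denominator makes this worse, because the size and even the direction of the between-arm difference depend on which one the programmer picks. Participants with a normal baseline value in a lineage cannot have HI in it, and eligibility does not require a cytopenia in any particular lineage. An mITT denominator would therefore also dilute the rates.

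The CMH comparison of HI rates is a separate mismatch. SAP section 4 undertakes to explain changes from the protocol's methods, and the changes listed in SAP section 8 do not mention this one. Section 8.3 refers to a separate Version 2.0 amendment summary that is not among the documents.

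**Working it through.** The documents give no HI rate and no mCR or PR rate, and the design CR rates are redacted, so there is no plan figure to reproduce. The check is algebra with a labelled illustration.

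**Symbols, for one lineage and one arm**
- R = proportion with CR, PR or mCR
- g = proportion with lineage HI among those
- h = proportion with lineage HI among the rest

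**Formulas**
1. HI counted in everyone: R×g + (1−R)×h
2. Restricted numerator over mITT: (1−R)×h
3. Restricted numerator over non-remitters: h

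**Assumed inputs (none from the documents).** R = 50% tamibarotene vs 30% placebo; g = 70% and h = 20% in both arms; everyone abnormal in the lineage at baseline.

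| Display | Tamibarotene | Placebo |
|---|---|---|
| 1. Everyone | 0.50×0.70 + 0.50×0.20 = 45.0% | 0.30×0.70 + 0.70×0.20 = 35.0% |
| 2. Restricted, over mITT | 0.50×0.20 = 10.0% | 0.70×0.20 = 14.0% |
| 3. Restricted, over non-remitters | 20% | 20% |

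With 190 participants (protocol 9.4.2) split 2:1, about 127 and 63, row 2 is roughly 12.7/127 vs 8.8/63. A 10-point advantage in row 1 becomes a 4-point deficit in row 2 and disappears in row 3.

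**When row 2 favours the arm with fewer remissions.** This happens when (1−R_T)×h_T < (1−R_C)×h_C, that is, when h_T/h_C < (1−R_C)/(1−R_T), with T for tamibarotene and C for placebo.

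| Remission, T vs C (assumed) | Threshold for h_T/h_C |
|---|---|
| 40% vs 30% | 0.70/0.60 = 1.17 |
| 50% vs 40% | 0.60/0.50 = 1.20 |
| 50% vs 30% | 0.70/0.50 = 1.40 |
| 60% vs 40% | 0.60/0.40 = 1.50 |

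At 50% vs 30%:
- h = 25% vs 20% (ratio 1.25, below 1.40) gives 12.5% vs 14.0%, still reversed, against 47.5% vs 35.0% when everyone is counted.
- h = 30% vs 20% (ratio 1.50, above 1.40) gives 15.0% vs 14.0%, not reversed.

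**Baseline-normal participants.** Suppose only half are abnormal in the lineage (assumed), equally in both arms and unrelated to remission. An mITT denominator then halves every figure: row 2 becomes 5.0% vs 7.0%. This changes size, not direction.

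**Which denominator the SAP implies.** For mITT: the default in 7.4.1, and the fact that a restricted denominator is written out for cytogenetic CR. Against: the clause about participants who failed remission can itself be read as the denominator, and SAP 7.1.1 has a general rule that a subcategory is summarized over participants in its parent category. The text does not settle it.

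**The case against.** The strongest reply is that the reversal depends on a denominator the SAP never states. With non-remitters as denominator it vanishes, as row 3 shows. Under the 7.1.1 rule with HI as the parent category, the lines would merely divide HI responders by lineage. This stands: a reader might infer that the SAP definitely counts these categories over all mITT participants and so will show a reversal, but 7.4.5.2 does not say so. Even over mITT, enough extra HI among non-remitters on tamibarotene removes it.

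A second reply is that HI and count recovery remain visible elsewhere. The individual HI rate carries no restriction, mCR is split by HI, CR requires recovered counts, and SAP 7.4.5.1 reports RBC and platelet transfusion independence in mITT. This also stands. A reader might infer that the SAP has replaced the protocol's HI rate with the restricted one. It has not, and the protocol plans no lineage rates.

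A third is that the restriction is declared in the wording, and a line for HI without remission is legitimate as a component of best response. That is fair, but it justifies keeping the line for that purpose, not using it as the only lineage display.

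Finally, the CMH omission applies equally to the CR/PR and CR/PR/mCR rates in protocol 9.4.4. It is a separate mismatch and no evidence of reversal.

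**Conclusion.** The concern holds for the lineage breakdown only. As written, the breakdown selects on a treatment outcome and has no stated denominator, so under no reading does it measure the treatment effect on counts:
- Over mITT, the arm with more remissions can show less lineage HI unless HI among non-remitters is sufficiently higher in that arm: by a factor of 1.17 to 1.50 across the remission rates tried.
- Over non-remitters, nothing reverses mechanically, but the groups compared are not randomized and count recovery in remission responders is left out.

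Every rate used here is assumed, and the reversal is conditional on the mITT denominator. The display is descriptive and affects neither CR, ORR, OS nor alpha. The unexplained loss of the CMH comparison of HI rates stands regardless of the denominator, subject to the amendment summary that could not be seen. This is an inexpensive improvement to a secondary display, not a threat to the trial's conclusions.

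**What to change.** In SAP 7.4.5.2:
- Report HI-E, HI-P and HI-N regardless of CR, PR or mCR status. Use as denominator the mITT participants with that lineage abnormal at baseline by the SAP's own criteria: hemoglobin below 11 g/dL or RBC-transfusion dependence; platelets below 100 × 10⁹/L or platelet-transfusion dependence; ANC below 1.0 × 10⁹/L.
- Restore the stratified CMH comparison of the overall HI rate from protocol 9.4.4, or record and justify its removal in section 8.
- Keep HI without CR, PR or mCR only as a labelled component of best response, with its denominator stated.

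The cost is SAP wording and programming. SAP 7.3.4 already tabulates the three baseline count thresholds, transfusions are recorded from 16 weeks before randomization, and SAP 7.4.6.7 already defines baseline transfusion dependence. The downside is that the lineage lines will not add up to ORR, so the two displays need separate labels.
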